1.1 Purpose of the Study

The primary aim of the proposed research is to evaluate the effectiveness of a self-guided, cognitive behavioral therapy (CBT)-based mobile app (SparkRx) + assessment-enhanced Usual Care (eUC) compared to eUC alone as an intervention for adolescents with symptoms of depression who are under the supervision of a licensed healthcare provider.

This aim will be accomplished by evaluating:

- A statistically significant difference in Patient Health Questionnaire (PHQ-8) scores ($p < 0.05$) between SparkRx + eUC (hereafter referred to as “SparkRx”) and eUC alone at post-intervention as a primary outcome. The Patient Health Questionnaire (PHQ-8) is provided in Appendix 1.
- Secondary/other outcomes of intervention response, remission, intervention safety based on participant adverse events and adverse device effects, anxiety symptoms, and global functioning, as well as retention rates, program adherence, and usability ratings. 1 month follow-up data will also be evaluated.

1.2 Background

1.2.1 Adolescent depression is a major public health concern

Depression, the most common mental health disorder among adolescents and young adults, is a critical health problem within the US, ranking 4th in global burden of disease^{1,2}. Annual incidence of a major depressive episode among adolescents is ~3.2 million, affecting 13.3% of teenagers and increasing to 26% when including mild depressive symptoms³. Rates of adolescent depression are rising sharply, with global prevalence of depressive symptoms estimated to have doubled over the past few years⁴. There has also been a 56% increase in adolescent suicides in the last decade, making suicide the #2 cause of death amongst teens⁵⁻⁷. These alarming trends highlight an urgency to develop effective and accessible treatments for affected adolescents⁴. Adolescent depression has far-reaching consequences including impairments in academic and work performance and social and family relationships, substance abuse, and exacerbation of other health conditions⁸⁻¹⁵. Affected youth are also at a higher risk for developing a range of other mental health disorders, as well as for unemployment and physical health problems in adulthood¹⁶⁻¹⁹. Adolescent depression places significant economic burdens on the US healthcare system²⁰, with higher medical costs than those for almost any other mental health condition²¹. Lastly, depression is a pervasive disorder^{22,23}, with lifetime recurrence rates of ~70%^{24,25}, and a \$210B societal burden annually as a whole, thus targeting this problem in adolescence, the typical time of initial onset, is critical for improving future outcomes. The proposed study is significant as it will target a critical public health concern, the urgency of which is now magnified by a global pandemic and mandated social distancing²⁶⁻²⁸, that impacts a significant proportion of the population and is presently a leading cause of global disability in youth²⁹.

1.2.2 Effective care for adolescents with symptoms of depression is limited

Adolescents with symptoms of depression constitute a large group with significant unmet clinical needs. Despite high prevalence rates of depression among adolescents, very few seek treatment and they are more prone to discontinue or reject psychotherapy, due to concerns over privacy and/or stigma^{30,31}. In addition, access to effective mental health care is often limited³²⁻³⁴. Demand for mental health professionals has outstripped supply, particularly in rural areas, a problem that is predicted to intensify over the next 10 years³⁵⁻³⁸. Waitlists for mental health providers are often at least 2-6 months long and represent one of the most substantial barriers to receiving care³⁹⁻⁴⁴. Consequently, 60-80% of adolescents with depression do not receive appropriate or timely treatment^{45,46}. Mandated social distancing practices implemented during the COVID-19 pandemic magnified the already significant challenges^{47,48}. Digital intervention is a solution that is needed immediately. Primary care visits provide a unique opportunity to identify adolescents with depression and direct them towards appropriate treatment. Primary care physicians often serve as a gateway for mental health treatments as official American Academy of Pediatrics guidelines recommend annual depression screening of

adolescents in primary care⁴⁹. However, many primary care providers lack adequate time and training to provide effective psychotherapy-based treatment and approved options for pharmaceutical treatments within adolescent populations are limited, have limited effectiveness⁵⁰⁻⁵² and may pose safety concerns in youth, including side effects in 10-25% of users^{53,54}. 50% of adolescents decline antidepressant use and only about a third of youth adhere to prescribed antidepressant therapy after it has been initiated in a pediatric setting^{55,56}. These significant barriers highlight a critical need and opportunity for new and effective treatment options for adolescent depression that can be prescribed by primary care providers. An evidence-based, self-guided psychotherapy delivered via a prescription product and overseen by a pediatrician can be a promising adjunct to standard of care with few anticipated side effects and can overcome existing limitations in access to mental health care, adherence, and safety.

1.2.3 Digital Interventions for Symptoms of Depression in Adolescents

Accumulating evidence highlights the efficacy of digital health interventions for mental illness, providing cost-effective, convenient, and accessible means of treatment⁵⁷⁻⁵⁹. Digital treatments via mobile applications hold particular promise for adolescent mental illness, as youth increasingly report high levels of smartphone use⁶⁰ and enjoy using novel technologies⁵⁷. Digital interventions can be completed at home, allowing patients to practice implementation of clinical recommendations⁶¹ and increasing accessibility of on-demand resources. Critically, such interventions can serve as a first line of defense for treatment, reducing⁵⁷ high economic costs associated with traditional in-person psychotherapies and wait times to access clinically-validated treatment. Digital health interventions can also be less stigmatizing, leading to higher rates of engagement and self-disclosure⁶²⁻⁶⁵. Mobile applications allow for delivery of interactive content, information collection, self-report, and remote patient monitoring, which can be harnessed to personalize and enhance treatment and to intervene appropriately. The recent COVID-19 global pandemic has further underscored the urgency for safe, accessible, and effective digital alternatives to standard mental health treatments⁶⁶⁻⁶⁹. This need is critical for the adolescent population who are especially vulnerable to depression and suicidality following environmental stressors, trauma, and social isolation^{28,48,70-74}.

Cognitive-behavioral therapy (CBT) is effective in the prevention and treatment of depression in children and adolescents⁷⁵⁻⁸⁰ and a recommended form of treatment by the American Academy of Pediatrics⁸¹. Digital forms of CBT⁷⁵⁻⁸⁰, have been shown to be effective in the treatment of anxiety and depression in youth⁸². Behavioral Activation (BA)⁸³⁻⁸⁷, a core CBT skill, seeks to 1) increase engagement with adaptive and contextually relevant activities that induce feelings of mastery or pleasure, 2) advance an individual's personal goals using a combination of motivational strategies, reward-seeking, natural reinforcers, and self-monitoring, and 3) reduce harmful and avoidant behaviors that often manifest during depressive episodes^{83, 84, 86, 87}. Adolescents may be especially vulnerable to reward-related deficits due to immaturities in reward processing neural systems^{88,89}, impacting their ability to both experience reward and overcome avoidance. BA can also be helpful in treating symptoms that especially impact adolescents with depression, including withdrawal from social activities, inactivity, and avoidance⁹⁰. BA-specific therapy offers a promising approach for treating depression in adolescents⁹¹⁻⁹³. Given that BA is necessarily individually paced, self-driven, and self-monitored, it can be easily delivered digitally, which may be appealing to depressed youth who have limited access to or interest in traditional care. Recent evidence suggests that behavioral aspects of CBT are equally effective as cognitive approaches in reducing depressive symptoms in youth and may mechanistically drive symptomatic reduction in CBT^{77,80, 89,94}. A digital BA program for adolescents with symptoms of depression represents an exciting new direction for treatment^{82,95, 96}. We hypothesize that the quantity and quality of behavioral activations completed by adolescents may mechanistically explain symptom improvement in response to a digital behavioral activation focused digital intervention.

Limbix Health Inc. / 1.0 4

Despite reported benefits and preliminary efficacy of digital health interventions in clinical research, the rigor of previous research is problematic as studies have suffered from small sample sizes and widespread adoption of and adherence to such interventions in clinical practice is limited⁹⁷⁻⁹⁹. Treatments developed in research settings are incongruous with those developed for commercial use, with the former lacking engaging content

and accessibility and the latter lacking an adequate evidence base. To our knowledge, there are no commercially available interventions nor prescription digital therapeutics specific to adolescents with symptoms of depression. We hypothesize that leveraging engaging mobile technologies will enhance treatment engagement and adherence, mediating clinical effectiveness, and ultimately reducing costs and wait times for mental health treatment for patients, closing a significant treatment gap in the care of adolescents with symptoms of depression.

2. Criteria for Subject Selection

2.1 Number of Subjects

220

Sample size calculation is based on primary outcome PHQ-8 at post-intervention. Six PHQ-8 measurements will be collected from each subject (baseline and weekly during the 5-week intervention period). Using a two-sample t-test approach, assuming a two-tailed alpha set at 0.05, a total of 200 participants (100 in each study arm) will give us 80% power to detect a moderate effect size of at least $d=0.4$. Given an anticipated 10% rate of attrition, we aim to enroll 220 total participants in the study.

2.2 Sex of Subjects

A 50% female sample will be targeted. Earlier recruitment efforts within the study demographic have resulted in majority female samples, consistent with prevalence rates within the study population. As such, recruitment efforts will be undertaken to ensure representation of male participants.

2.3 Age of Subjects

13-21 years old. Adolescent depression is on the rise, which can have deleterious effects on healthy transitioning to adulthood, with prevalence rates highest within this age range. The age group selected is expected to have the capacity to complete a self-guided intervention program. Recruitment efforts will be taken to ensure equivalent representation of participants under and over the age of majority (18 years old).

2.4 Racial and Ethnic Origin

Recruitment efforts will be taken to ensure adequate representation of underrepresented racial and ethnic minority groups.

2.5 Inclusion Criteria

1. 13-21 years of age
2. PHQ-8 score ≥ 5 at eligibility screening
3. English fluency and literacy (participant and legal guardian, if applicable)
4. Access to a compatible smartphone (or other device) and operating system (i.e., capable of installing the app from the Google Play or Apple App Store; list will be provided on study website [app2]) and regular internet access
5. Participant willing and able to provide informed consent/assent and have legal guardian willing and able to provide informed consent (if required)
6. Under the care of a United States (U.S.)-based licensed healthcare provider and willing and able to provide contact information for the provider and sign a HIPAA release that allows Limbix to contact provider
7. Willing and able to provide information required for study enrollment (e.g. all responses to initial PHQ-8 assessment, and current antidepressant medication status)
8. Located in the continental U.S., Hawaii, or Alaska, and not planning to leave the U.S. during the study period (through 1-month follow up assessments, up to 11 weeks after eligibility screening)

2.6 Exclusion Criteria

1. Diagnosis of (or treatment for) bipolar disorder, post traumatic stress disorder, psychotic disorder, substance use disorder, or eating disorder within the 12 months prior to eligibility screening
2. Change in psychotropic medication (initiation or change in dose) within the 30 days prior to eligibility screening
3. Plans to initiate or change treatment (e.g., psychotherapy, psychotropic medication, and/or other psychosocial treatment) for a mental health disorder during the study intervention period (5 weeks) as determined at eligibility screening
4. Suicide attempt within the past year
5. Active suicide ideation with intent
6. Previous participation in user testing or clinical testing of Spark or SparkRx, or other previous use of SparkRx app
7. Participation in any other clinical research involving a mental health intervention or treatment within 60 days prior to eligibility screening
8. Plans to participate in any other clinical research involving a mental health intervention or treatment during the study intervention period (5 weeks) as determined at eligibility screening
9. Any condition, comorbidity, or event that, in the opinion of the investigator, will prevent the participant from adhering to the protocol or benefitting from the intervention (e.g., coercion, low level of cognitive functioning) or will prevent investigators from being able to ensure safety (e.g., will be leaving the country during study time period)
10. Having a sibling who is a past or current participant in the study

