SparkRx group: The SparkRx mobile program will be 5 weeks in duration and self-guided. The five modules in this program are each expected to take around 60 minutes to complete. Modules do not need to be completed in a single session but can be completed over the course of several days. Emergency resources for participants experiencing thoughts of suicide or self-harm will be available in the app. While participants can progress through the programs at their own pace, participants will be instructed to complete one module in the mobile app per week, and to complete the program within the 5-week intervention period. Participants will be prompted to complete weekly PHQ-8 and PSC in the mobile application. App notifications, text (SMS) and/or email messages may be sent to participants to encourage them to complete the weekly assessments (i.e., PHQ-8 and PSC). To encourage participants to engage with the app, automated app notifications will also be sent. For participants under 18 years of age, legal guardians may receive email and/or text notifications to complete proxy PHQ-8 and PSC assessments in the secure web portal.

eUC group: Participants will download a mobile app that contains no content, but that provides access to in-app weekly PHQ-8 and PSC assessments.

All participants will receive notifications (app notifications and SMS and/or email) to complete the PHQ-8 and PSC). For participants under 18 years of age, legal guardians may receive email and/or text notifications to complete proxy PHQ-8 and PSC assessments in the secure web portal .

Post-intervention period

After the 5-week intervention period, all participants will be sent links via email and/or text to complete post-intervention self-report questionnaires in the secure web portal. Participants may receive automated email and text reminders to complete the post-intervention questionnaires. A study coordinator may also contact participants (and legal guardians) who have not completed post-intervention questionnaires before they reach a 2 week deadline.

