One month after the end of the intervention period, participants will be prompted to complete self-report questionnaires to evaluate sustained effects of the intervention on relevant outcomes. Participants may receive automated email and text reminders to complete the questionnaires. A study coordinator may contact participants (and legal guardians) who have not completed follow-up questionnaires before they reach a 2 week deadline. Participants who do not complete the one-month follow-up questionnaires within 2 weeks will be considered lost to follow-up.

If a participant chooses to withdraw from the study at any point or the participant is dropped from the study during the intervention period (5 weeks), access to the web portal and mobile app will be restricted at that time; otherwise access to the mobile app will be restricted at the end of week 5 and access to the web portal will be restricted after 1-month follow-up assessments have been completed or the participant is deemed lost to follow-up.

All relevant FDA requirements for the conduct of clinical trials will be followed, including registration on clinicaltrials.gov. Email and other notification templates are provided in Appendix 6.

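### Exclusion 8 ends at week 5, so a declared plan to join another mental-health intervention study in week 6 does not bar entry, although outcomes are collected up to week 11

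*Combined protocol and SAP*

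**What the plan says.** Section 2.6 looks both backward and forward at other research. Exclusion 7 rules out: "Participation in any other clinical research involving a mental health intervention or treatment within 60 days prior to eligibility screening". Exclusion 8 rules out: "Plans to participate in any other clinical research involving a mental health intervention or treatment during the study intervention period (5 weeks", judged at eligibility screening. Exclusion 3, on planned treatment starts or changes, has the same end point: "for a mental health disorder during the study intervention period (5 weeks) as determined at eligibility screening".

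Outcome collection continues after that point. Section 3.1 states: "After the 5-week intervention period, all participants will be sent links via email and/or text to complete post-intervention self-report questionnaires". Coordinators may chase those "who have not completed post-intervention questionnaires before they reach a 2 week deadline". One month after the intervention period, "participants will be prompted to complete self-report questionnaires to evaluate sustained effects of the intervention on relevant outcomes"; Table 1 places this 4 weeks after the intervention, and Section 3.1 allows a further 2 weeks before a participant counts as lost to follow-up. Table 1 lists the PHQ-8 and the Participant Symptom Check (PSC) weekly, at post-intervention and at 1 month.

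One criterion does use the whole period. Inclusion 8 (Section 2.5) requires that the person is "not planning to leave the U.S. during the study period (through 1-month follow up assessments, up to 11 weeks after eligibility screening".

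Section 3.1 also asks participants to report, in the weekly PSC or directly to the study team, if they take part in another treatment or intervention study.

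**The concern.** As written, a candidate can say at screening that they will start another depression-intervention study in week 6 and still satisfy exclusion 8. Exclusion 9 leaves room for investigator judgement but does not name this situation. Scores given after the person joins would then count as SparkRx or eUC outcomes.

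Nothing later in the plan picks this up. The intention-to-treat analysis keeps everyone. The per-protocol set (Section 4.7.1) requires only the baseline and post-intervention PHQ-8 and, for SparkRx, two completed modules. The planned sensitivity analyses concern departures from missing at random. The primary model (Section 4.7.2) uses the actual completion day as time, so a late score enters like any other. Reports of joining another study are requested, but no analysis uses them.

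What is at stake is mainly how the 1-month comparison is read. It is meant to show whether the effect of SparkRx lasts, and another intervention begun between week 5 and week 11 blurs that reading.

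**Working it through.** **1. Reproduce the plan's own window.** Screening, baseline and randomisation belong to one enrolment process that Section 3.1 describes around a single video session, so weeks are counted from there.
- Post-intervention: 5 weeks + 2-week deadline = week 7 (day 49).
- 1-month follow-up opens: 5 + 4 = week 9. It closes: 5 + 4 + 2 = week 11 (day 77).

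The 11 weeks match inclusion 8 exactly.

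**2. Compare with the bar in exclusion 8, which ends on day 35.**
- Latest post-intervention score: 49 − 35 = 14 days uncovered; 14/49 = 29%.
- Latest follow-up score: 77 − 35 = 42 days uncovered; 42/77 = 55%.

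These are worst-case shares of calendar time. They are not shares of participants or scores, nor a measure of bias.

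**3. Which outcomes are exposed?**
- Primary: Section 4.1 labels the time point as 5 weeks, and Section 4.6 counts only baseline and weekly PHQ-8 scores. Exposure is limited to people who complete the portal PHQ-8 late, in weeks 5 to 7, and who have already joined another study. The plan does not say whether the week-5 in-app score or the portal score is the primary one; if it is the in-app score, exposure is smaller still.
- 1-month: the whole window, weeks 9 to 11, lies outside the bar. Section 4.3 classes these outcomes as tertiary/exploratory.

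**4. What would balanced joining do?** Plans are judged before 1:1 randomisation, so the expected proportion of planners, p, is the same in each arm. Suppose that among joiners the SparkRx–eUC difference shrinks by a fraction k. The overall difference is then d × (1 − p × k). If the outside intervention simply adds the same benefit in both arms, k = 0 and the mean difference is unchanged. If it removes the difference among joiners, k = 1.

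For reference, the plan's sizing reproduces: d = 0.4 at two-sided 0.05 needs 99.1 per arm by t-test, so 100, and power at 100 per arm is 0.804. The table takes the worst case, k = 1. The values of p are assumptions.

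| p | d × (1 − p) | Power, 100 per arm |
|---|---|---|
| 0 | 0.400 | 0.804 |
| 2% | 0.392 | 0.788 |
| 5% | 0.380 | 0.762 |
| 10% | 0.360 | 0.717 |
| 20% | 0.320 | 0.615 |

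With k = 0.5 and p = 10%, the loss is 0.10 × 0.5 = 5%, so the 5% row applies. The table only shows scale: the 1-month comparison is not the one the trial was sized for.

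**5. Added noise.** If joiners shift by δ points, the variance rises by p(1 − p)δ². Assuming p = 10%, δ = 2 and SD = 5: 0.10 × 0.90 × 4 = 0.36, and 0.36/25 = 1.4%. That is minor.

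**6. Which scores could a sensitivity analysis catch?** Someone who joins in week 6 before completing the portal set first reports it on the post-intervention PSC, collected with the post-intervention PHQ-8. Someone who joins after that first reports it on the 1-month PSC, collected with the 1-month PHQ-8. A rule that drops only scores after the report would remove no post-intervention score affected by joining after week 5. It would catch a 1-month score only where joining had already been reported at post-intervention. The rule has to read at or after.

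**The case against.** The strongest reply is that ending the bar with the intervention is a coherent choice. App access also stops at week 5. The location rule in inclusion 8 lasts longer because safety monitoring needs it (Sections 3.1 and 7.3), so its 11 weeks do not show that exclusion 8 was meant to match. Usual care (Section 3.3) already allows psychotherapy, medication and other support in both arms, so outside treatment is part of the contrast, and closing the research route alone gains little. Intention-to-treat is itself a rule for these scores: they are kept.

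Most of this stands, and it limits the weight of the point. Inclusion 8 supplies ready wording rather than proof of an error. What is missing is a supplementary analysis, not a rule for handling the scores. But exclusion 7 shows that the sponsor regards other intervention research as relevant to this trial even up to 60 days before screening. Admitting someone with a declared plan for week 6 sits awkwardly beside that.

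A further objection is that eUC participants, whose app has no content, might look for another study after week 5, and that a criterion on plans at screening cannot prevent this. That is correct: such joining is a decision made after randomisation, and it needs the supplementary analysis rather than the eligibility change.

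**Conclusion.** The gap is in the text: the bar ends at week 5, while outcomes run to week 7 and then through weeks 9 to 11. It matters mainly for the exploratory 1-month comparison, and for the primary outcome only among late completers. Because plans at screening are balanced in expectation, the main expected effect is dilution and noise. Its size depends on p and k, which the documents do not give.

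A reader might infer more: that eUC participants will join other studies more often, so that the results are biased toward no difference by a calculable amount. The documents do not support this. They give no uptake rate in either arm. An illustration with 5 to 15 percentage points more joining in eUC and an outside benefit of 2 points gives 0.05 × 2 = 0.1 to 0.15 × 2 = 0.3 points. Set against a trial effect also taken as 2 points (0.4 × an assumed SD of 5), that is 5% to 15%, which only returns the assumed uptake difference. Differential joining is plausible, but its size and direction cannot be computed. Nor can a reader conclude that the primary result is broadly contaminated.

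This is a small improvement worth making because it costs almost nothing.

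**What to change.** - **Exclusion 8:** replace the five-week limit with the period in inclusion 8, so that the bar covers plans up to the end of the 1-month assessments, at most 11 weeks from screening. Change the screening script to match.
- **Analysis plan:** keep intention-to-treat as primary. Add a supplementary sensitivity analysis of the post-intervention and 1-month PHQ-8 comparisons that sets aside scores recorded at or after the assessment whose PSC first reports joining another intervention study. State that it conditions on an event after randomisation and so does not replace the primary result. Section 4.7 leaves the detailed SAP to be written before primary data collection ends, so this can be pre-specified there.
- **Form check:** confirm that the post-intervention and 1-month PSC ask about joining other studies. Section 3.1 mentions the weekly PSC for this, and the form itself is in an appendix.
- **Exclusion 3:** it has the same five-week end date. The sponsor should reconcile it with the assessment schedule; no rule is proposed here.

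Cost: one phrase in the criteria, one extra analysis on reports the plan already asks for, and a few people with plans for weeks 6 to 11 becoming ineligible. The sample size does not change.
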